Pancreas divisum is overrepresented in patients with iRAP (Fischer, Hassan et al. 2010, Gono, Akai et al. 2011) and pancreatitis susceptibility mutations such as in the cystic fibrosis transmembrane conductance regulator (*CFTR*) gene (Bertin, Pelletier et al. 2012, Ballard, Flueckiger et al. 2015). Some have hypothesized that divisum protects against exocrine pancreas insufficiency during youth, and then later in life predisposes to RAP in patients with susceptibility mutations (Nicholson, Johnstone et al. 2012). The association between divisum and susceptibility mutations does not refute the potential benefit of miES in reducing the risk of future acute pancreatitis or other RAP sequelae. A sham controlled, randomized trial will be the ideal format for the careful collection of data on known and potential covariates. Other than pancreatitis susceptibility mutations, potential covariates that might impact the natural history of iRAP with pancreas divisum include smoking, age, number of previous attacks, main pancreatic duct diameter, and presence of definite chronic pancreatitis morphology. This study protocol will exclude patients with RAP who have obstructive chronic pancreatitis (e.g., main duct strictures or stones) since treatment of these entities would not address the overarching question of this study: does miES reduce the risk of acute pancreatitis in patients with iRAP?

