6.3 Discussion regarding enrollment criteria

Exclusion criteria 2 and 3. Using these criteria, it is possible that some patients with early chronic pancreatitis will be included. We will capture this information and consider appropriate secondary per protocol analyses; however, the primary analysis will be intention to treat which will include all randomized subjects. Moreover, in the absence of calcifications, we will not exclude patients based on the number of EUS findings - rather, we will record the number and type of EUS criteria present, and during analysis determine if the number of EUS findings is a prognostic variable. We elected deliberately not to use the Cambridge classification system since "moderate" changes of chronic pancreatitis by this system include irregularity and dilation of the main pancreatic duct. For example, the presence of a Santorinicele (focal cystic dilation of the distal portion of the dorsal pancreatic duct, at the minor papilla) might be interpreted in this category. These individuals represent an important subgroup who may benefit from miES. Main pancreatic duct diameter – and the presence of a Santorinicele – will be measured in all subjects and is considered in the randomization scheme.

Inclusion criterion 4. Requiring at least one attack in the previous 24 months: In clinical practice, it is uncommon for a patient with RAP to present for ERCP in the absence of having an episode in the past 24 months. This criterion will assure that subjects randomized in SHARP have an adequate baseline incidence rate of acute pancreatitis episodes

Exclusion criterion 6. Patients will be queried about their use of pain medications in the preceding 3 months. This criterion is meant to minimize the risk of enrolling subjects with chronic pain, in whom minor papilla sphincterotomy is not expected to help and in whom future endoscopic or surgical interventions are more likely. Since these subsequent interventions would adversely impact the ascertainment of the primary outcome, these patients will be excluded.

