9. STUDY PROCEDURE

9.1 Baseline Assessments

In addition to assessments related to eligibility, all patients will be administered the following questionnaires prior to the EUS:

- Demographics
- Previous pancreatitis episodes
- Smoking and alcohol use history
- Pancreatitis risk factors
- Pertinent medication utilization
- Quality of life (PROMIS29 and PROMIS Global)
- Pain assessment and related disability (PROMIS Nociceptive & Neuropathic Pain), and
- Opioid and other pain medication use

Information about the subject's medical history, including information about past pancreatitis episodes and pancreatitis risk factors will be collected from the subject's medical record.

If the subject has not already been diagnosed with diabetes mellitus, an assessment for diabetes mellitus will be performed at baseline (fasting or random blood glucose and hemoglobin A1c). If the subject has not been diagnosed with exocrine insufficiency, subjects will undergo fecal elastase testing during the baseline assessment. The diagnosis of diabetes mellitus will be established by use of antidiabetic medications or when a patient has abnormal values on two of the following tests or two abnormal values of the same test: a) fasting blood sugar ≥ 126 mg/dl; b) HbA1c $\geq 6.5\%$; c) random blood sugar ≥ 200 mg/dl.

The diagnosis of exocrine pancreatic insufficiency will be established by a clinical history suggestive of steatorrhea, quantitative fecal fat > 7 g/day, or fecal elastase concentration <100 mcg/g of stool. See Biospecimen SOPs for details of sample collection, shipping, storage and testing.

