15. STATISTICAL CONSIDERATIONS

15.1 Sample Size and Power Estimation

Since the natural history of iRAP is poorly understood, risk estimates are based on previous small clinical trials and epidemiological studies. Based on a previous small trial of ERCP for RAP in pancreas divisum with limited (1-year) follow-up for the majority of patients, the probability of developing a third episode of AP is 70%.(Lans, Geenen et al. 1992) Natural history studies specific to divisum are lacking, but retrospective cohort studies and one surgical series suggest the recurrence rate following minor papilla stenting, miES, or surgical sphincteroplasty are 15-50%(Attwell, Borak et al. 2006, Chacko, Chen et al. 2008, Borak, Romagnuolo et al. 2009, Crino, Bernardoni et al. 2017). Given the short-term risk of post-ERCP pancreatitis (~10%), costs of ERCP, and potential for post-sphincterotomy re-stenosis, we believe a minimum effect size of 33% (relative risk reduction) is of clinical relevance. This effect size was agreed upon by the site principal investigators as the least clinically significant benefit for ERCP, considering the risks of ERCP and available data on this topic. Since AP recurrence is variable and time sensitive, we propose a reduction in risk of subsequent acute pancreatitis during follow-up as the primary outcome, defined by the median time to acute pancreatitis recurrence (a time-to-event measure). We assume the risk of recurrence within 12 months of randomization is 60% in EUS + sham and 40% in EUS + ERCP with miES groups, with the median time to recurrence being 9.1 and 16.3 months for EUS + sham and EUS + ERCP with miES groups, respectively. Assuming an exponential hazard, a 2-sided alpha error of 5%, power 85%, and non-adherence of 20% (this includes technical crossovers when sphincterotomy cannot be performed and competing events/risks), the trial requires a total sample size of approximately 234 (n=117 per group).

We recognize that sample size estimation is based on assumptions and if the event rate is lower than assumed, we may begin to see a decrease in power. To reduce the likelihood of an underpowered study due to incorrect assumptions, a sample size re-estimation will be conducted during the enrollment period. Details of this plan as well as all statistical considerations are outlined in the SHARP Statistical Analysis Plan.

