15.3 Statistical Analyses

The primary analysis of the trial will be done in accordance with the "intent-to-treat" (ITT) principle, *i.e.*, all randomized participants will be included in the analysis. This means that once a participant is randomized to an intervention group, the participant's data will be included in the primary analysis regardless of compliance with the protocol-specified intervention or follow-up requirements.

A cox-proportional hazards model will be used to assess time to first occurrence of acute pancreatitis (primary outcome). Subjects without an outcome event will be censored at the last known status or at the end of study time point. We will adjust for duct diameter and number of attacks in the past 24 months in the primary analysis. Additional analyses will explore the impact of the other potential prognostic variables. This study is designed to test the primary hypothesis. However, it also offers the opportunity to conduct analyses to evaluate important additional patient outcomes. Details of the full analysis plan are in the Statistical Analysis Plan document.

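### Smoking, age and a defined EUS morphology variable could be prespecified in the primary Cox model: a cheap efficiency gain of unknown size, not an error in the stated 85% power

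*Combined protocol and SAP*

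**What the plan says.** Section 15.3 specifies a Cox model for time to first acute pancreatitis and states "We will adjust for duct diameter and number of attacks in the past 24 months in the primary analysis". Other prognostic variables are left to additional exploratory analyses. The two chosen covariates are also minimization factors in 15.2, together with site.

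Section 3.7.2 gives a longer list: "potential covariates that might impact the natural history of iRAP with pancreas divisum include smoking, age, number of previous attacks". It continues with main pancreatic duct diameter and definite chronic pancreatitis morphology. Two of these five clinical items are in the primary model and three are not.

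The data for the remaining three are collected before randomization. Section 9.1 lists "Smoking and alcohol use history" and demographics among the items taken before the EUS. Section 9.2 has the endoscopist complete a standardized record of parenchymal and ductal changes during the EUS. On the number of EUS findings, section 6.3 says the investigators will "during analysis determine if the number of EUS findings is a prognostic variable".

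Section 15.1 assumes "risk of recurrence within 12 months of randomization is 60% in EUS + sham and 40% in EUS + ERCP with miES groups", with "median time to recurrence being 9.1 and 16.3 months" in the sham and miES groups respectively. The calculation is introduced by "Assuming an exponential hazard, a 2-sided alpha error of 5%, power 85%, and non-adherence of 20" per cent and arrives at 234 patients. It takes no account of covariates. Sections 15.1 and 15.3 refer to a separate Statistical Analysis Plan for full details; its contents are not in the text reviewed.

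**The concern.** In a Cox model, leaving out a covariate that predicts the outcome pulls the estimated treatment hazard ratio towards 1 and lowers power, even when the arms are balanced on it. Adjusting for a baseline variable that turns out not to matter costs very little. The protocol has three such variables named and recorded, and does not use them in the primary test. Minimization does not cover them either, so neither the design nor the primary model deals with a chance imbalance in smoking, age or EUS findings.

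At stake is power that needs no further patients, in a trial that section 5.3 expects to recruit 3 to 4 patients per site per year. The sample size re-estimation in 15.1 is motivated by a lower event rate, which is a different problem.

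**Working it through.** **Inputs from the protocol.** Two-sided alpha 5%, power 85%, exponential hazards, 12-month risks 60% and 40%, medians 9.1 and 16.3 months, non-adherence 20%, N = 234 (15.1); 1:1 allocation (15.2); accrual over 42 months and follow-up of 6 to 48 months (5.4).

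**Step 1: reproduce the stated sample size without covariates.**
- Hazard ratio from the risks: ln(0.6)/ln(0.4) = 0.557. From the medians: 9.1/16.3 = 0.558. They agree.
- Schoenfeld events: 4(1.960 + 1.036)²/(ln 0.557)² = 105.2, rounded up to 106.
- Event probability with uniform accrual: 1 − [exp(−6λ) − exp(−48λ)]/(42λ), with λ = ln 2/median. This gives 0.810 for sham and 0.639 for miES, mean 0.725.
- 106/0.725 = 146.3. Treating non-adherence as dilution of the effect, 146.3/(1 − 0.2)² = 229.
- The Lachin-Foulkes formula gives 153.3, and 153.3/0.64 = 240.

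Both are within 3% of 234. The protocol does not state its inflation rule. Dividing by 0.8 only once gives 183, so the squared form is inferred from the fit.

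**Step 2: power at N = 234 without covariates.** Events: 234 × 0.7245 = 169.5. Diluted hazard ratio: 0.557^0.8 = 0.627. Power: Φ(√169.5/2 × |ln 0.627| − 1.960) = 86%, against 85% stated.

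**Step 3: value of the three extra terms.** The documents give no hazard ratio or prevalence for these factors, so the following are assumptions: 40% smokers, 25% with the morphology feature, age standard normal, all independent. Duct diameter (hazard ratio 1.2 per SD) and number of attacks (1.5) are prognostic and are in both models. Randomization is simple 1:1, and follow-up is uniform on 6 to 48 months. The whole-arm 12-month risks are held at the planning values after dilution: 60% for sham and 1 − 0.4^0.627 = 43.7% for miES. There are 8,000 simulated trials per row.

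| Assumed HR: smoking / age per SD / morphology | Power, planned model | Power, three terms added | Change (points) |
|---|---|---|---|
| 1 / 1 / 1 (none) | 87.7% | 87.4% | −0.3 |
| 1.2 / 1.1 / 1.2 (weak) | 87.0% | 87.4% | about +0.5 |
| 1.5 / 1.2 / 1.5 (moderate) | 86.4% | 89.3% | +2.9 |
| 2 / 1.3 / 2 (strong) | 84.9% | 92.1% | +7.2 |
| 2.5 / 1.6 / 2.5 (very strong) | 82.6% | 95.4% | about +13 |

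The Monte Carlo standard error of one power figure is about √(0.87 × 0.13/8000) = 0.4 point. Allowing for variation between repeat runs, the gain is best quoted as about 0 (weak), 3 to 4 (moderate) and 7 to 8 (strong), with a loss of at most about 1 point if nothing is prognostic. In the table's runs the moderate and strong gains equal what about 10% and 27% more patients would give.

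**Step 4: same simulation, but with 0.627 taken as the effect within covariate strata (5,000 trials each).** Planned-model power becomes 85.8%, 85.5%, 81.2%, 75.0% and 66.2% down the same rows, against about 85% with the three terms added. This reading is taken up in the objection.

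**The case against.** A reader might infer from Step 4 that the trial falls short of its 85%. The documents do not support that. Section 15.1 sets the effect through whole-arm 12-month risks and medians, which already average over smokers, ages and morphology. Reading the implied hazard ratio as covariate-specific builds in the attenuation that is then reported as a loss. With the whole-arm risks held fixed, the planned model stays at about 85% or above up to the strong scenario, and drops to 82.6% only in the very strong one. A separate run with 30% smokers and a treatment-only model gave 85.9% (smoking HR 1.5), 85.3% (HR 2.0), 85.2% (HR 1.5 plus other covariates with log-hazard SD 0.2) and 83.9% (HR 2.0 plus SD 0.3).

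Three further objections stand:
- **Prognostic value is not asserted.** Section 3.7.2 speaks only of possible influence, 6.3 leaves the value of EUS findings open, and 15.1 calls the natural history poorly understood.
- **Morphology is not absent from the model.** Duct diameter is a morphology measure and is included. Excluding calcific disease and main duct stricture (6.2) narrows what remains, although 6.3 accepts that some early chronic pancreatitis will be enrolled.
- **The two-covariate model is a legitimate choice.** It is short, prespecified and tied to the minimization factors.

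A reader might also infer that the primary analysis is open to choice after outcomes are seen. It is not. Section 15.3 fixes its covariates, and the later exploratory analyses cannot alter the primary test. How those are prespecified in the separate SAP cannot be judged here.

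None of this removes the case for adding the terms: they are named, recorded before randomization and nearly free to include.

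**Conclusion.** The point holds as a cheap improvement. The primary model omits three potential covariates that the protocol itself names, and smoking, age and EUS morphology are available before randomization. The size of the gain cannot be known from the documents. It depends on assumed prognostic strengths and prevalences, independent covariates, simple randomization in place of minimization, and non-adherence acting as effect dilution. On that footing the gain is negligible for weak predictors and becomes material only if they are strong, while the downside stays small. The stated sample size and power are consistent with the protocol's own assumptions and need no correction.

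**What to change.** Before unblinding, amend 15.3 and the SAP so that the primary Cox model contains:
- duct diameter;
- number of attacks in the past 24 months;
- smoking status;
- age;
- one defined baseline EUS morphology variable, for example the count of EUS criteria.

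Fix the coding of each in advance: smoking categories, the form of age, and how the EUS variable enters. Report the two-covariate model as a sensitivity analysis. If the separate SAP already specifies these terms, 15.3 only needs to be reconciled with it.

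Cost: no new data and no extra patients. It is a protocol wording change, so section 16.2 requires prior IRB approval. The added terms use three degrees of freedom with binary smoking and linear age and EUS count, or four if smoking has three levels. The expected number of events is about 234 × 0.710 = 166 to 234 × 0.725 = 170.

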15.4 Observational Cohort

The observational cohort will aid in the interpretation of the findings of the randomized study. We are most interested in comparing the two cohorts, randomized and observational, in terms of baseline characteristics that may cause bias. These comparisons will be primarily descriptive. Two-sided 95% confidence intervals will be constructed and hypothesis tests will be conducted at an alpha level of 0.05.

Based on data from other endoscopic and surgical studies with sham arms, and correspondence with some of the authors(Larson, Blute et al. 1998, Moseley, O'Malley et al. 2002, Salem, Rotevatn et al. 2004, Cotton, Durkalski et al. 2014), we anticipate that anywhere between 25-50% of eligible subjects will decline to participate in the randomized study. A sample size of 100 for the observational cohort was chosen based on enrollment projections for the randomized trial.

16. REGULATORY AND ETHICAL OBLIGATIONS

16.1 Informed Consent

It is the investigator's responsibility to ensure that informed consent is obtained from the participant before participating in an investigational study, after an adequate explanation of the purpose, methods, risks, potential benefits and participant responsibilities of the study. Procedures that are to be performed as part of the practice of medicine and which would be done whether or not study entry was contemplated, such as for diagnosis or treatment of a disease or medical condition, may be performed and the results subsequently used for determining study eligibility without first obtaining consent. On the other hand, informed consent must be obtained prior to initiation of any screening procedures that are performed solely for the purpose of determining eligibility for research.

Each participant must be given a copy of the informed consent. The original signed consent must be retained in the institution's records and is subject to review by the

sponsor, DCU, representatives from regulatory agencies, and the IRB responsible for the conduct of the institution.

Informed consent will be obtained by either the Principal Investigator or by individuals approved by the Clinical Center's Principal Investigator and whose names have been submitted to DCU. Informed consent will be obtained from the participant after the details of the protocol have been reviewed. The individual responsible for obtaining consent will assure, prior to signing of the informed consent, that the participant has had all questions regarding therapy and the protocol answered.

16.2 Single Institutional Review Board (SIRB)

In accordance with US federal regulations and ICH Good Clinical Practice Consolidated Guideline) all research involving human subjects and changes to the research plan must be reviewed and approved by an IRB.

Per NIH policy (<https://grants.nih.gov/grants/guide/notice-files/NOT-OD-16-094.html>), the Medical University of South Carolina Institutional Review Board will serve as the Single Institutional Review Board for all participating U.S. sites. The **Single Institutional Review Board (SIRB)** for multicenter protocols is the single IRB of record.

The Medical University of South Carolina IRB will initiate reliance agreements with each relying institution. The relying institution will be responsible for performing a local context review of the study to ensure that the protocol is appropriate and reasonable for their respective study populations.

Each relying site must undergo SIRB review and obtain SIRB approval before initiating any study activities at the site. SIRB approved study materials (such as informed consent documents, patient-facing materials, etc.) will not be provided to a site until that site has received SIRB approval.

Study wide amendments and/or modifications to the study will not be initiated without prior written approval of the SIRB except when necessary to eliminate immediate hazards to patients.

17. ADMINISTRATIVE AND LEGAL OBLIGATIONS

17.1 Study Termination

The study will be complete when all subjects have had their final study assessments. The Sponsor or Executive Committee reserves the right to terminate the study if new information becomes available on the safety or efficacy of the study product or if such action is justified.

If the study is terminated, the investigator will provide any outstanding data or documentation related to the study at the time.

The Clinical Center reserves the right to terminate the study according to the contract. The SHARP PIs are responsible for notifying the SIRB in writing of the trial's completion or early termination. A copy of the notification must be uploaded into the regulatory database as part of the study regulatory documents.

17.2 Study Documentation and Storage

Source documents are the original or valid records of participant information from which case report form data are obtained. These include, but are not limited to, reports of test results, hospital charts and medical records, and correspondence. Case report form entries may be considered source data if the case report form is the site of original notation, such as the patient questionnaires or quality of life instrument.

In June 2005, a new Federal law was implemented that extends the statute of limitations to six (6) years to bring forward an allegation of research misconduct. In response to this extension, research records must be retained for a sufficient period to investigate an allegation of research misconduct - **a minimum period of six (6) years**. An agreement must be in place between the Site Investigator and the Principal Investigator regarding records that may be destroyed.

17.3 Publication Policy

Investigators will be offered the opportunity to publish as a group or with recognition of individual authors. This decision will be made before analyses are conducted. Refer to the study Publication Policy for more details.

